2 ABSTRACT

Catheter ablation with pulmonary vein (PV) isolation is a commonly performed strategy employed for the treatment of atrial fibrillation (AF). However, ablation in the posterior wall of the left atrium can cause thermal injury to the esophagus. Thermal injury is very common and occurs in up to 40% of AF ablations per some studies. When significant thermal injury to the esophagus occurs, two significant complications can arise: 1) the formation of an atrio-esophageal fistula, and 2) gastrointestinal dysmotility. While the occurrence of fistula is rare, it is a very important complication since it is often fatal. Currently luminal esophageal temperature monitoring is the most commonly employed modality to prevent such injury. However, there are

limitations to its use, and atrio-esophageal fistulas continue to be a major problem in AF ablation even when using esophageal temperature monitoring. Esophageal deviation using either a Transesophageal echocardiogram (TEE) or Esophagogastroduodenoscopy (EGD) probe has been described in the literature, but the effectiveness and practicality of these techniques are suboptimal, and have therefore precluded their use in routine clinical practice. Recently, esophageal deviation using off-the-shelf equipment (a soft thoracic tube and endotracheal stylet) was tested in the randomized double-blind multicenter study “Deviating the Esophagus in Atrial Fibrillation Ablation (DEVIATE-AF)”. In that study the standard practice (i.e., use of luminal esophageal temperature monitoring) was compared to esophageal deviation using off-the-shelf equipment. The results were very encouraging showing that esophageal deviation allowed for significant reductions in esophageal temperature and proportion of premature ablation terminations. Importantly, esophageal deviation allowed the isolation all PVs in the treatment group, which was not the case in the control group. One major limitation in the DEVIATE-AF trial was that off-the-shelf equipment tool was challenging to use. The aim of the Esophageal Deviation in Atrial Fibrillation Ablation study is to test the feasibility and safety of moving the esophagus using a specialized esophageal deviation tool (DV8, Manual Surgical Sciences, Minneapolis, MN).

3. STUDY OBJECTIVE

Catheter ablation is a commonly performed procedure employed for the treatment of drug resistant atrial fibrillation (AF). For paroxysmal AF, the ablation typically involves pulmonary vein (PV) isolation, and in cases of persistent AF often involves additional linear ablation lesions, ablation of sites of complex fractionated atrial electrograms (CFE), and ablation of drivers of AF. However, when ablation lesions are placed in the posterior left atrial (LA) wall during the above-mentioned steps, these lesions can cause thermal injury to the adjacent esophagus. This can result in 1) esophageal erosions and/or ulcers – which can culminate in fatal atrio-esophageal fistula formation, and 2) gastrointestinal dysmotility such as gastroparesis as a result of damage to the peri-esophageal vagal plexus.

To minimize the chance of these complications, electrophysiologists employ different strategies to minimize esophageal injury. A widely accepted and recommended strategy is to deploy a transnasal or transoral temperature sensing probe into the esophagus to detect esophageal heating during ablation; this allows the physician to either modulate the level of energy used or to terminate any individual ablation lesion that results in inappropriate heating of the esophagus. While this approach has been shown to reduce esophageal injury, it is clear that this is an imperfect tool as evidenced by the reporting of both ulcerations and fistula formation in patients with no detectable temperature rise. In addition, even if the detection of esophageal temperature rise is identifiable in all cases, this still necessitates that the operator stop ablation and wait for the temperature to passively cool before applying another ablation lesion. This adversely impacts procedure time, and (by allowing time for tissue edema to form between lesion applications) might even impact on the long-term durability of the PV isolating lesion set.

Recently, the randomized double-blind multicenter study “Deviating the Esophagus in Atrial Fibrillation Ablation (DEVIATE-AF) demonstrated that the esophagus can be successfully displaced in patients undergoing AF ablation using off-the-shelf equipment (a soft thoracic tube and endotracheal stylet). One major limitation in the DEVIATE-AF trial was that off-the-shelf equipment tool was challenging to use. The aim of the Esophageal Deviation in Atrial Fibrillation Ablation study is to test the feasibility and safety of moving the esophagus using a specialized esophageal deviation tool (DV8, Manual Surgical Sciences, Minneapolis, MN).

4 INTRODUCTION, RATIONALE, PRELIMINARY DATA

Introduction and Rationale:

Role of catheter ablation: Atrial fibrillation (AF) is a disorder affecting more than 3 million Americans. The likelihood of developing AF increases with age. Three to five percent of people over 65 have AF. Given the aging population, it is important that effective therapeutic strategies are available. Non-pharmacologic approaches to maintaining sinus rhythm with catheter ablation offer an alternative approach for control of AF and avoid the toxicity of anti-arrhythmic drugs. Several randomized controlled trials have demonstrated the superiority of catheter ablation over medical treatment for AF, in terms of maintenance of sinus rhythm and improved symptoms (1,2,3,4,5). PV isolation is a procedure that involves placing circumferential and importantly transmural lesions around all the PVs to electrically isolate the veins from the rest of the left atrium (LA). This procedure alone is successful for 70–90% of patients with paroxysmal AF (6), the effectiveness largely depending on the contiguity and transmurality of these circumferential lesions around the PV. Catheter ablation of persistent AF on the other hand usually involves a hybrid strategy, incorporating PV isolation with further ablation, typically in the form of linear lesions, complex fractionated electrogram ablation, and/or ablation of drivers of AF that need to be performed in various locations in the LA including the posterior wall of the LA (7,8) which lies in close proximity to the esophagus.

[figure not shown]
Gastro-esophageal injury: While the overall complication rates of catheter ablation of AF have decreased (major complication rates in large centers are in the 2-3% range) with advancements in technique and technology of catheter ablation, the threat of gastro-esophageal damage due to thermal injury from ablation remains. In fact, the risk of atrio-esophageal fistula formation remains one of the most dreaded complications of catheter based AF ablation today.

Thermal injury during AF ablation can occur in the form of esophageal erythema, hemorrhage, erosions, ulceration, gastro-esophageal motility disorders or rarely atrio-esophageal fistulas. These occur consequent to the use of thermal based ablation applied to the posterior wall that often lies immediately adjacent to the esophagus (9,10). It is thought that this thermal energy extends beyond the posterior LA wall and reaches the adjacent esophagus causing damage that manifests as described above. In patients undergoing radiofrequency (the most common thermal based energy source) catheter ablation of AF, the reported incidence of any esophageal injury varies from 2.2% - 48%. The incidence of the often catastrophic atrio-esophageal fistula however, is much lower at around 0.04% (11). Typically, the clinical presentation of such fistulae occurs late after the procedure (usually within the first 2 weeks) (9,10). The symptoms are usually nonspecific, including fever, neurological abnormalities, gastrointestinal bleeding, and sepsis. This condition is often fatal. The mechanism of esophageal injury is thought to be to thermal injury (9,10,12,13). The degree of variation in the reported incidence of esophageal damage (2.2- 48%) is likely accounted for by differences in the frequency of use of esophageal protection (e.g. - temperature monitoring probe), use of general anesthesia versus conscious sedation, magnitude of power, duration and contract force during ablation and finally the method of assessment of esophageal injury. An effective strategy to reduce gastro-esophageal injury is therefore of significant clinical importance.

[figure not shown]
Esophageal protection strategies: Several strategies have been described to help prevent or reduce gastro-esophageal injury during AF ablation. These include luminal esophageal temperature (LET) monitoring (14), determination of the anatomical relationship of the esophagus to the posterior LA with pre-procedural or real time imaging (15,16,17) and modulation of power and duration of radiofrequency lesions (18). The effectiveness of the above approaches, even when applied in combination, has failed to prevent atrio-esophageal fistula formation (17). Moreover, these strategies do not address the need for reduction of other forms of injury, such as gastroesophageal motility disorders that originate from injury of vagal nerves that surround the esophagus. In addition, LET monitoring focuses on the early detection of thermal injury, and both 1) invariably results in a pause in ablation while waiting for passive tissue cooling, and 2) often results in modification of the lesion sets, i.e., by directing the encircling lesions to be either more ostial or further midline in order to avoid temperature rises. Such modifications increase the risk of vein stenosis and the formation of 'gaps' that may reduce the long-term clinical success of the ablation procedure. Frequent premature lesion terminations and power reductions may also compromise chronic PV isolation rates, an endpoint critical to the long-term outcomes of AF ablation.

Autopsy studies (19) have shown that there is loose areolar tissue between the anterior wall of the esophagus and the parietal pericardium of the posterior left atrium. A post-mortem study (19) demonstrated that the esophagus relative to the posterior left atrium could be displaced up to 7 cm. Both these studies indicate that lateral esophageal displacement is a feasible strategy from an anatomic basis. Lateral mechanical displacement of the esophagus along the posterior LA as an esophageal protective strategy has been previously described using either an endoscope (20) or a TEE (21). Both these strategies had significant limitations. In the strategy using the endoscope, i) the actual deviation of the esophagus was unclear since concomitant contrast was not employed to differentiate esophageal deviation from esophageal tenting, ii) the esophagus could not be deviated in 2/12 patients, and most importantly, iii) the deviation could not be maintained in 7 patients to allow uninterrupted lesion delivery. This approach required the active participation of a gastroenterologist and the true extent of deviation achieved was unclear given the lack of barium contrast. On the other hand, in the strategy using the TEE probe, all 3 patients underwent successful displacement that was maintained during ablation, but this was not studied in a systematic fashion. Although thought-provoking, widespread application of these two techniques has not been realized in clinical practice due to attendant limitations. Over the past 2 years the randomized double-blind multicenter study "Deviating the Esophagus in Atrial Fibrillation Ablation (DEVIATE-AF) demonstrated that the esophagus can be successfully displaced in patients undergoing AF ablation using off-the-shelf equipment (a soft thoracic tube and endotracheal stylet) (Figure-1). The study randomized 69 patients and is still ongoing. Interim analysis revealed that esophageal deviation allowed for significant reductions in maximum esophageal temperature rises { $1.1\pm 0.7^{\circ}\text{C}$ vs $0.26\pm 0.2^{\circ}\text{C}$, $p<0.0001$ } and proportion of premature ablation terminations { $38.8\pm 0.3\%$ vs $5.7\%\pm 0.1$, $p<0.0001$ }. Importantly, all PVs were not isolated in 2 controls due to temperature rises. In the deviation arm, total time and RF time for PV isolation was shorter, but did not reach statistical significance. There were challenges however related to the ease of deviation using the off-the-shelf tool, and it was concluded that the technique requires improvement.

Figure-1: Off-the-shelf tapered tip (solid arrows) thoracic catheter used for esophageal deviation. Adjacent to that is an endotracheal stylet with a distal curve (dashed arrows)

Because of the logistical difficulties attendant with the off-the-shelf tools and the obvious need that remains in terms of esophageal protection during AF ablation, we sought to evaluate the feasibility and safety of a strategy of mechanical esophageal deviation during AF ablation using specialized equipment (DV8 specialized esophageal retractor tool made by Manual Surgical Sciences, Minneapolis, MN) (Figure-2). **The device is commercially available in the US and is 510(k) exempt. (Regulation Number 878.4800, Registered Establishment Number is 3011596926)** **Figure-2:** DV 8 esophageal retractor.

The DV8 Retractor™ Esophageal Balloon (DV8 Retractor) is a non-sterile, single-use, disposable esophageal balloon retractor. It is deployed orally and inflated inside the esophagus. The retractor gently and effectively retracts the esophagus to create a stable operating field. The DV8 Retractor has a marker band located at the proximal waist and double marker bands located at the distal waist of the balloon, which are distinguishable from each other under fluoroscopic visualization. When the procedure is completed, the device is deflated and removed. Each balloon inflates to its stated diameter and length at 4-8ATM of pressure. The balloon diameter is $\pm 10\%$ at the nominal pressure. The Rated Burst Pressure (RBP) is 16

atmospheres (ATM). The DV8 Retractor is designed with a silicone sleeve and balloon coupled to a fitting that can attach to a syringe with a pressure gauge. The DV8 Retractor also has a fitting that allows attachment of a syringe to inject contrast medium directly into the esophagus. The device is 61 cm in length and the balloon is 15 cm balloon length. When inflated, the balloon diameter is 14mm. The detailed steps for deployment are as follows:

[figure not shown]
Insertion and Inflation:

- The DV8 Retractor Esophageal Balloon is removed from its package. The Inflation Syringe is filled with pressure gauge with an appropriately diluted (25-50%) contrast medium (Gastrografin).
- The Luer-tip Inflation Syringe is attached with pressure gauge into the DV8 Retractor balloon inflation stopcock.
- Lubricant is applied to the balloon and device shaft. The DV8 Retractor is directed into the esophagus using fluoroscopic guidance.
- The balloon is positioned in the appropriate location with the distal marker band at the level of the lower esophageal sphincter.
- The balloon is inflated with contrast medium with 4-8 ATM of pressure as indicated on the Inflation Syringe (Figure-3).

Deflation and Withdrawal:

- The balloon is deflated prior to withdrawing from the esophagus.
- The deflated DV8 Retractor Balloon is withdrawn from the esophagus using a smooth, gentle, steady motion.

Figure-3: X ray images of the DV8 retractor before and after inflation.

Preliminary data:

The esophagus was successfully displaced using the DV8 retractor in over 200 patients worldwide. Eleven cases have been performed at MGH. No complications have been reported with its use. In a cohort study at Mt. Sinai Medical Center in New York, 47 patients underwent esophageal deviation using the DV8 tool and were compared with 114 patients who underwent deviation using the off-the-shelf stylet. All procedures were performed under general anesthesia. The extent of deviation, as measured by the distance between the trailing edge of the esophagus and the ablation points, was significantly larger with the DV8 tool (Figure-4). Moreover, the incidence of esophageal temperature rises was higher with the off-the-shelf technique compared to the DV8 retractor (Figure-5). Another preliminary study was conducted by the Mt-Sinai group in order to assess the optimal distance for esophageal movement that eliminates the chance of heating. It showed that if the esophagus is moved by an average of 2 cm from the ablation site, no significant heating occurs (Figure-6)

Figure-4: Comparison of the extent of deviation between the DV8 retractor and off-the-shelf stylet.

[figure not shown]

Figure-5: Comparison of the incidence of esophageal temperature rise between the DV8 retractor and the off-the-shelf stylet.

[figure not shown]
[figure not shown]

Figure-6: Incidence of esophageal temperature rise at different distances from the area of ablation.

These data demonstrate the feasibility and safety of the novel technique of esophageal deviation that facilitates uninterrupted energy delivery to the posterior wall during AF. It also demonstrated that the esophagus needs to be moved by an average of 2 cm in order for heating not to occur. Although the results have been very encouraging with respect to safety and efficacy, we believe that there is value in an additional study to prove the reproducibility of the findings.

We propose a prospective single-arm study to confirm the safety and feasibility of this novel deviation tool.

5 ENDPOINTS

5.1 PRIMARY CLINICAL ENDPOINT

The following primary endpoint will be assessed:

- 1) The extent of esophageal deviation as measured by the incidence of successfully moving the esophagus to achieve a minimum distance of 1 cm between the ablation line for the ipsilateral PV pairs and the trailing edge of the esophagus.

5.2 SECONDARY CLINICAL ENDPOINTS

The following secondary endpoints will be assessed:

1. The extent of esophageal deviation as measured by the incidence of successfully moving the esophagus by an average of 2 cm from the ablation line for the ipsilateral PV pairs.
2. The incidence of esophageal laceration as assessed by a Barium swallow study performed within 1-3 days of the procedure.
3. Incidence of PV reconnection at 30 min post-ablation
4. Fluoroscopy time
5. Procedure duration
6. Time from start of ablation to last ablation lesion for pulmonary vein isolation

The deviation distance was based on the preliminary study mentioned above, showing that if the esophagus is moved by an average of 2 cm, no significant heating occurs.

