7.2 STOPPING CRITERIA

STOPPING CRITERIA

We propose as a stopping criterion the occurrence of 1 case or more of esophageal laceration based on the finding of the Barium Swallow.

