9.2 POST-PROCEDURE

9.2.1 POST-PROCEDURE TESTING

- Swallowing impairment score: next morning

- Preferably the next day but up to 3 days after the procedure: Barium swallow to be performed on all patients.

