9.2.3 POST-PROCEDURE MEDICATION MANAGEMENT

- All medications are left up to the discretion of the investigator.
- Visualization of any esophageal injury should prompt proton pump inhibitors for 2 weeks (per usual practice of the clinical site), CT scan of the chest, and referral to the gastroenterology service.
- Therapeutic anticoagulation (example warfarin or equivalent agent) is at the discretion of the patient's electrophysiologist.

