9.3.1 ADVERSE EVENTS

The incidence of serious adverse events over the course of the study will be recorded. An adverse event is any undesirable clinical occurrence in a study patient, whether or not it is related to the study intervention. Any condition that was recorded as pre-existing is not an AE unless there is a change in the nature, severity or degree of the condition.

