9.4 RISKS

As the protocol described is standard to an AF ablation procedure, the risks of the procedure include that of a standard AF procedure, which are:

Common:

- Discomfort at the site of venous access
- Groin hematoma

Uncommon:

- Discomfort in the throat region
- Cardiac Perforation requiring drainage or surgery
- Pulmonary venous stenosis / occlusion
- Thrombus formation / stroke
- Injury to adjacent structures (phrenic nerve, esophagus, lung, cardiac valves)
- Bleeding

- Congestive heart failure
- Renal dysfunction
- Vascular complications (including pseudoaneurysm, AV fistula requiring surgical intervention)
- Myocardial infarction
- Esophageal deviation risks include dental injury and esophageal injury similar to that of TEE
- Radiation burns
- Ventricular arrhythmias or QT prolongation
- Pneumonia and/or sepsis
- Anaphylaxis
- Death

Additional risks unique to the protocol are

- Sore throat
- Aspiration pneumonia from barium sulfate or Gastrografin.
- Difficulty or painful swallowing
- Bleeding from the mouth area or from the food pipe
- Perforation—a tear or hole in the esophagus (the “tube” that connects your mouth to your stomach”) or heart
- Infection
- Failure to protect the esophagus from heat related injury.
- Nausea
- Abdominal pain
- Atrio-esophageal fistula- An abnormal connection between the atria of the heart and the esophagus in which they fuse together

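### The only esophageal safety endpoint counts laceration alone, so other injury seen on the same barium swallow has no prespecified place in the results

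*Combined protocol and SAP*

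**What the plan says.** The plan has one primary and six secondary endpoints. Only one of the seven measures harm to the esophagus, item 2 of section 5.2, repeated in Appendix 2: "The incidence of esophageal laceration as assessed by a Barium swallow study performed within 1-3 days of the procedure". Section 9.2.1 makes the test universal: "Barium swallow to be performed on all patients". The stopping criterion in section 7.2 rests on the same finding: "We propose as a stopping criterion the occurrence of 1 case or more of esophageal laceration based on the finding of the Barium Swallow".

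Elsewhere the protocol works with a wider category. Section 9.2.3, also copied in Appendix 2, states "Visualization of any esophageal injury should prompt proton pump inhibitors for 2 weeks", together with a chest CT and a gastroenterology referral. Section 4 describes the harm that motivates the device: "Thermal injury during AF ablation can occur in the form of esophageal erythema, hemorrhage, erosions, ulceration, gastro-esophageal motility disorders or rarely atrio-esophageal fistulas". Section 9.4 includes, among the risks particular to this protocol, perforation and "Failure to protect the esophagus from heat related injury".

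On adverse events, section 9.3.1 gives a broad definition: "An adverse event is any undesirable clinical occurrence in a study patient, whether or not it is related to the study intervention". The incidence it commits to is narrower: "The incidence of serious adverse events over the course of the study will be recorded".

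**The concern.** The study is proposed in order to confirm the safety and feasibility of the retractor. Its single esophageal safety endpoint is narrower than the injury category that the same protocol uses for patient care, and narrower than the list of harms in its own rationale. An ulcer visible on the swallow would score the same on endpoint 2 as a normal study.

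What is at stake is how the safety result reads. A zero on the laceration endpoint could be presented as the esophageal safety finding of the trial although some patients had injury visible on study imaging and were managed for it. Nothing in the plan obliges the report to show those patients in a table.

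**Working it through.** The plan states no figure for this endpoint. Its only design calculation concerns the primary endpoint, and this point does not depend on it. The check is therefore mainly a comparison of sections.

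**Categories side by side**

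| Place | Finding used |
|---|---|
| 5.2 item 2 and Appendix 2 (endpoint) | laceration on barium swallow |
| 7.2 (stopping criterion) | laceration on barium swallow |
| 9.2.3 and Appendix 2 (management) | any visualized esophageal injury, modality not named |
| 4 (rationale) | erythema, hemorrhage, erosion, ulceration, motility disorder, fistula |
| 9.4 (risks particular to the protocol) | includes perforation, fistula, failure to protect from heat injury |

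Laceration is not in the section 4 list, and no section defines it. The exclusion criteria in 6.2 list ulcers, bleeding, laceration and perforation as separate items, so the authors do distinguish these terms.

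**Is there another guaranteed route into the results?**

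- 9.3: adverse events and serious adverse events are monitored and reported to the IRB. That is oversight, not a prespecified result.
- 9.3.1: an incidence is promised for serious adverse events only. Under 9.3.2, whether a non-life-threatening, non-disabling ulcer is serious depends on the investigators' opinion.
- 9.3.3: capture covers adverse events defined by the protocol. No list follows. If the general definition in 9.3.1 is meant, the text does not say so.
- 7: only the primary-endpoint calculation and the stopping criterion appear. No adverse-event analysis is described.
- The Swallowing Impairment Score is collected at baseline, the next morning, 2 weeks and 3 months (9.1.1, 9.2.1, 9.2.2), but it is not an endpoint.

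So injury other than laceration may be recorded, but no section ensures that it is summarized.

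**Size**

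Inputs: N = 64 (6.1); background rate of any esophageal injury after radiofrequency ablation 2.2% to 48% (section 4); follow-up above 95% (section 8).

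1. Endpoint as written with no laceration: upper exact two-sided 95% limit = 1 − 0.025^(1/64) = 5.6%, so 0/64 has CI 0 to 5.6%. With 61 evaluable patients (0.95 × 64 = 60.8), the limit is 1 − 0.025^(1/61) = 5.9%.
2. Background arithmetic: 64 × 0.022 = 1.4 and 64 × 0.48 = 30.7 patients, if deviation gave no protection. This is not a forecast of swallow findings. Section 4 itself attributes the spread partly to the method of assessment; the range is for radiofrequency, whereas 9.1.2 allows any thermal system; and nothing says what share barium would show.
3. Illustration under an assumed 1 to 6 visible non-laceration injuries (no source in the documents), with Clopper-Pearson limits:

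| Visible injuries | Laceration endpoint | Any visible injury (95% CI) |
|---|---|---|
| 1 | 0/64 | 1.6% (0.04 to 8.4%) |
| 3 | 0/64 | 4.7% (1.0 to 13.1%) |
| 6 | 0/64 | 9.4% (3.5 to 19.3%) |

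**The case against.** The strongest defense is that laceration is the right choice for this device. A balloon retractor does its direct harm mechanically; thermal protection is the efficacy rationale and is addressed through the distance endpoints. The documents do not say that barium shows erythema, erosion or ulcer. In a single arm, a count of thermal injuries cannot separate the device from the ablation. All of this is fair. It is a reason to keep laceration as a named component and to state the limits of a wider count, but not to leave visible injury out of the results of a safety study.

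Four stronger readings are tempting, and the documents do not support them.

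- A reader might infer that non-laceration injury can never reach the reported safety result. The adverse-event definition in 9.3.1 is broad, events are monitored and sent to the IRB, and causality is judged separately for ablation and deviation (9.3.4). Such an injury may well be recorded; what is missing is the guarantee that it will be summarized.
- A reader might infer that a leak would score as no laceration. The term is undefined, so a leak might count. The gap is the missing definition.
- A reader might infer that 9.2.3 refers to the swallow and covers dysmotility. It names neither. Appendix 2 speaks of storing a copy of an endoscopy where 9.2.4 speaks of the barium swallow, and no endoscopy is scheduled, so the intended modality is unclear.
- A reader might take the background range as the size of a bias. For the reasons given in the working, it cannot carry that weight.

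**Conclusion.** The point stands in a limited form. The endpoint's numerator is narrower than the protocol's own injury category, and the plan gives non-laceration injury no prespecified or guaranteed place in the reported results. The trial could therefore report 0/64 (CI 0 to 5.6%) on its only esophageal safety endpoint while visible injuries occurred.

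This rests on the text alone. The number of patients affected is unknown; the 1.6% to 9.4% illustration rests entirely on the assumed 1 to 6 injuries. The primary analysis, sample size and power are not touched. The change is worth making because the test is already done on everyone and safety is a stated aim.

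**What to change.** In 5.2 item 2 and its copy in Appendix 2:

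- Keep laceration as a named component and define it, stating whether a leak or perforation counts.
- Add, as a descriptive secondary safety endpoint, the incidence of any esophageal injury seen on the day 1 to 3 barium swallow, by type (laceration, leak or perforation, ulcer or other mucosal injury), with an exact 95% CI and the number of patients imaged as denominator.
- State three limits: a swallow may miss superficial thermal lesions, so a zero is not evidence that none occurred; no baseline swallow is scheduled, so pre-existing findings cannot be separated from new ones; and a single-arm count does not separate device from ablation effects.
- Do not count a motility abnormality as new. Summarize changes in the Swallowing Impairment Score from baseline separately.

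A sentence in 9.3 should say which adverse events 9.3.3 means and how non-serious esophageal events will be tabulated.

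Sections 5.2 and 7.2 use one finding category and 9.2.3 another; the sponsor must reconcile them. No stopping or clinical rule is proposed here.

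The cost is a few lines of wording and one extra table from data already collected. The downside is a reported injury rate that may look less favorable than the laceration rate alone.
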